9.4.4 Safety Analyses

Safety endpoints include death through Day 29, SAEs and Grade 3 and 4 AEs. These events will be analyzed univariately and as a composite endpoint. Time-to-event methods will be used for death and the composite endpoint. Each AE will be counted once for a given subject and graded by severity and relationship to COVID-19 or study intervention. AEs will be coded using the current version of the Medical Dictionary for Regulatory Activities (MedDRA). AEs will be presented by system organ class, duration (in days), start- and stop-date. Adverse events leading to premature discontinuation from the study intervention and serious treatment-emergent AEs will be presented either in a table or a listing.

9.4.5 Baseline Descriptive Statistics

Baseline characteristics will be summarized by treatment arm. For continuous measures the mean and standard deviation will be summarized. Categorical variables will be described by the proportion in each category (with the corresponding sample size numbers).

9.4.6 Planned Interim and Early Analyses

Early analyses:

A blinded sample size re-estimation will be conducted after approximately 115 patients to evaluate the proportion of subjects who have recovered by Day 29, which will provide important information about the number of patients needed to achieve 400 recoveries. Additionally, the number of deaths will be evaluated.

Additional early analyses include monitoring enrollment, baseline characteristics, and follow-up rates throughout the course of the study by the study team. Analyses will be conducted blinded to treatment assignment.

Interim analyses:

A DSMB will monitor ongoing results to ensure subject well-being and safety as well as study integrity. The DSMB will be asked to recommend early termination or modification only when there is clear and substantial evidence of a treatment difference. More details about the interim

analyses are described in section 9.4.6.1 and 9.4.6.2 below as well as a separate guidance document for the DSMB.

9.4.6.1 Interim Safety Analyses

Safety analyses will evaluate Grade 3 and 4 AE and SAEs by treatment arm. Safety monitoring will be ongoing (see section 10.1.6) and evaluate safety results weekly. This approach is less conservative than what will be used to test for early efficacy results because proving definitive harm of the experimental agents is not the focus of this study. Pocock stopping boundaries at the looks described correspond to z-scores of (2.28, 2.29, 2.30). This contrasts with the z-score stopping boundaries for the Lan-DeMets spending function that mimics O'Brien-Fleming boundaries: (3.71, 2.51, 1.99). The unblinded statistical team will prepare these reports for review by the DSMB.

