9.4.6.2 Interim Efficacy Review

The Lan-DeMets spending function analog of the O'Brien-Fleming boundaries will be used to monitor the primary endpoint as a guide for the DSMB for an overall two-sided type-I error rate of 0.05. Interim efficacy analyses will be conducted after the blinded sample size re-estimation of the primary efficacy endpoint at approximately 33%, 67%, and 100% of total information.

Conditional power will be presented as an additional guide to the DSMB. Conditional power allows computation of the probability of obtaining a statistically significant result by the end of the trial given the data accumulated thus far, incorporating and assuming a hypothesized treatment effect (e.g., the treatment effect assumed for sample size determination) thereafter. If conditional power is less than 20% under the original trial assumptions, consideration should be given to stopping the trial.

The unblinded statistical team will prepare these closed reports for DSMB review and recommendations. Analyses will be presented with blinded codes for treatment arms to protect against the possibility that the DSMB report may fall into the wrong hands. A DSMB charter will further describe procedures and membership. An additional document on statistical issues related to monitoring will be provided to the DSMB prior to interim analyses.

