10.1.6.2 Data Safety Monitoring Board

Safety oversight will be conducted by a DSMB that is an independent group of experts that monitors subject safety and advises DMID. The DSMB members will be separate and independent of study personnel participating in this trial and should not have scientific, financial or other conflicts of interest related to this trial. The DSMB will consist of members with appropriate expertise to contribute to the interpretation of the data from this trial. The DSMB should be as broadly informed as possible regarding emerging evidence from related studies. The DSMB will operate under the guidelines of a DMID-approved charter that will be written at the organizational meeting of the DSMB. The DSMB will review SAEs on a regular basis and ad

hoc during this trial. The DMID Medical Monitor will be responsible for reviewing SAEs in real time. The DSMB will review SAEs on a regular basis and ad hoc during this trial.

The DSMB will conduct the following reviews:

- Electronic access to safety data after every 50 subjects are dosed. If this trigger occurs more frequently than every 4 weeks, then the meeting can be delayed until approximately 4 weeks after the last meeting.
- Formal reviews of safety/efficacy after approximately 200 subjects have met recovered status.
- Ad hoc meeting if the protocol team raises any concerns
- A final review meeting after final clinical database lock, to review the cumulative unblinded safety data for this trial.

The study will not stop enrollment awaiting these DSMB reviews, although the DSMB may recommend temporary or permanent cessation of enrollment based on their safety reviews.

Additional data may be requested by the DSMB, and interim statistical reports may be generated as deemed necessary and appropriate by DMID. The DSMB may receive data in aggregate and presented by treatment arm. The DSMB may also be provided with expected and observed rates of the expected AEs in an unblinded fashion and may request the treatment assignment be unblinded for an individual subject if required for safety assessment. The DSMB will review grouped and unblinded data in the closed session only. At each meeting, the DSMB will make a recommendation as to the advisability of proceeding with study interventions (as applicable), and to continue, modify, or terminate this trial.

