6.6. Interim Analyses and Data Monitoring

6.6.1. Interim Safety Analyses

Interim safety data will be available electronically in real time. No formal interim safety analyses are planned.

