6.6.2. Interim Efficacy Review

Interim efficacy analyses will be conducted after at approximately 50% of total information. The information fraction at an interim analysis will be computed as $t = r/400$, where r is the number of recoveries by the time of the data freeze date for the interim analysis. The Lan-DeMets spending function analog of the O'Brien-Fleming boundary will be used to monitor the

primary endpoint using an overall two-sided type-I error rate of 0.05. Specifically, two one sided boundaries are constructed at level 0.025 using the spending function

$$\alpha^*(t) = 2[1 - \Phi\{2.241/t^{\frac{1}{2}}\}],$$

where Φ is the standard normal distribution function. Lan-DeMets software from the University of Wisconsin, now available in the R package 'lrbounds', will be used to calculate boundaries.

Conditional power will be presented as an additional guide to the DSMB. Conditional power allows computation of the probability of obtaining a statistically significant result by the end of the trial given the data accumulated thus far, incorporating and assuming a hypothesized treatment effect (e.g., the treatment effect assumed for sample size determination) thereafter. If conditional power is less than 20% under the original trial assumptions, consideration should be given to stopping the trial.

The unblinded statistical team will prepare these closed reports for DSMB review and recommendations. Analyses will be presented with blinded codes for treatment arms to protect against the possibility that the DSMB report may fall into the wrong hands. A DSMB charter will further describe procedures and membership. An additional document on statistical issues related to monitoring will be provided to the DSMB prior to interim analyses.

Section 6.2.3 describes the plan for the final analyses of the early and final analysis sets.

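### The Pocock harm boundaries printed in Protocol 9.4.6.1 are calibrated to three looks at thirds of information, where no safety look is scheduled, and SAP 6.6.1 plans no formal interim safety analysis

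*Protocol*

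**What the plan says.** Protocol 9.4.6.1 covers interim safety. Grade 3 and 4 AEs and SAEs are compared by arm, and the section says: "Safety monitoring will be ongoing (see section 10.1.6) and evaluate safety results weekly". It explains that the approach is meant to be looser than the one for efficacy, and then states that "Pocock stopping boundaries at the looks described correspond to z-scores of (2.28, 2.29, 2.30"). It contrasts these with the O'Brien-Fleming-type efficacy bounds 3.71, 2.51 and 1.99. It lists no safety looks of its own and gives no error rate for safety.

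The other statements about looks are these:

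- Protocol 9.4.6.2 puts the efficacy analyses "at approximately 33%, 67%, and 100% of total information". Its spending function serves "as a guide for the DSMB for an overall two-sided type-I error rate of 0.05", for the primary endpoint.
- Protocol 10.1.6.2 gives the DSMB safety data after every 50 subjects dosed (a meeting may be put back to about 4 weeks after the last) and adds: "Formal reviews of safety/efficacy after approximately 200 subjects have met recovered status". The synopsis repeats this.
- Protocol 7.1.2 disclaims any pre-set rule for halting the study. The synopsis makes an exception for whatever appears under the DSMB.
- SAP 6.6.1: "No formal interim safety analyses are planned".
- SAP 6.6.2: "Interim efficacy analyses will be conducted after at approximately 50% of total information", with the information fraction defined as recoveries divided by 400.

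**The concern.** A group-sequential boundary means something only for the looks it was computed for. The three safety values belong to a schedule of thirds, but the formal safety and efficacy review is at about 200/400 = 50%, routine safety review is weekly or every 50 subjects, and the SAP has no formal safety analysis at all. A DSMB member reading the two documents cannot tell whether a harm boundary exists, at which looks it applies, to which endpoint, or at what error rate.

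The mismatch can also push in either direction. At fewer looks than three, the printed values are stricter than a Pocock-type guide at 5%, so a real harm signal has to be larger to cross. At many more looks, they are looser than they appear.

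**Working it through.** **Inputs.** Safety bounds 2.28, 2.29, 2.30 and efficacy bounds 3.71, 2.51, 1.99 (Protocol 9.4.6.1). Looks at 33%, 67% and 100% (Protocol 9.4.6.2). Formal review at about 200 recoveries (Protocol 10.1.6.2) out of a target of 400, so 50%. Two one-sided 0.025 boundaries for efficacy (SAP 6.6.2). The number of weekly reviews is not given and is assumed below.

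**Step 1: reproduce the printed bounds.** The Pocock-type spending function is α(t) = 0.05 × ln(1 + (e − 1)t), two-sided.

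- At t = 0.33, α = 0.05 × ln(1 + 1.718 × 0.33) = 0.0225. Half of this in each tail gives z = 2.283.
- Integrating the joint normal distribution recursively through t = 0.67 and t = 1 gives 2.291 and 2.297.
- The result 2.283, 2.291, 2.297 rounds to the printed 2.28, 2.29, 2.30. The printed values spend 0.0226, 0.0159 and 0.0116 at the three looks, about 0.050 in total, or 0.025 per side.
- The efficacy comparators also reproduce at exact thirds: 3.710, 2.511, 1.993.

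So both sets are correct for three looks at thirds. The 5% for safety is implied by this calculation; the protocol does not state it.

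**Step 2: the formal review at 50% plus a final look.**

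- α(0.5) = 0.05 × ln(1 + 1.718 × 0.5) = 0.0310, so the first bound is 2.157. The remaining 0.0500 − 0.0310 = 0.0190 gives a second bound of 2.201 (correlation between looks √0.5).
- With 2.29 at the first look and 2.30 at the final look, the first look spends 2 × P(Z > 2.29) = 0.0220 and the total is 0.0374, about 3.7% two-sided or 1.9% per side, against an implied 5% and 2.5%.
- At 50% of information the O'Brien-Fleming-type bound is 2.963, so even 2.29 would still be looser at the interim than the efficacy bound there, as the protocol intends.

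**Step 3: a constant 2.29 at K equally spaced looks, under no difference.** This is conditional on a use that the protocol does not describe.

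| K (assumed) | Two-sided crossing | Harm side only (about half) |
|---|---|---|
| 3 | 0.050 | 0.025 |
| 5 | 0.068 | 0.034 |
| 8 | 0.086 | 0.043 |
| 12 | 0.103 | 0.052 |
| 20 | 0.126 | 0.063 |

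If the looks were instead every 50 subjects, the two-sided figure would be 0.102 for 572 subjects (11 looks plus final) and 0.116 for 800 (16 looks). A constant bound that holds 0.05 two-sided would be 2.59 for 12 looks and 2.67 for 20.

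**The case against.** The best defence is that the z-scores were never meant as a weekly rule. Three values cannot serve weekly reviews, and the natural reading is that they refer to the three looks in the next section, since the efficacy values beside them use the same schedule. The passage may only illustrate how much looser the safety standard is meant to be. That looseness is deliberate and explained, Protocol 7.1.2 disclaims study halting rules, and Protocol 9.4.6 leaves detail to separate DSMB documents not available here. SAP 2.1 adds that interim details were left unmodified in version 3.0 because the DSMB meeting had already taken place.

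Most of this stands, and it rules out two stronger readings that a reader might infer. One is that the boundary fails a stated error rate for harm. The documents give no such rate: the two-sided 0.05 is for the primary efficacy endpoint, and the 5% for safety is only implied. The other is that the plan doubles the chance of a false harm signal. That requires 2.29 to be used at each weekly review, which no passage says, and an assumed number of looks.

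The defence does not remove the inconsistency. If the values refer to the looks in Protocol 9.4.6.2, those are efficacy looks, while Protocol 10.1.6.2 puts the formal safety and efficacy review at about 200 recoveries and SAP 6.6.2 puts the efficacy interim at about 50%. The protocol calls the values stopping boundaries in its section on interim safety, while SAP 6.6.1 plans no formal safety analysis. A separate DSMB document cannot settle a conflict between the protocol and the SAP.

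**Conclusion.** The point holds as a conflict between current passages. The printed safety boundaries are arithmetically right for looks at 33%, 67% and 100%, but they fit no safety look that the plan schedules, and the SAP has no formal safety analysis to which they could apply. At the one formal review plus a final look they would spend about 3.7% two-sided instead of the implied 5%, where matching bounds are 2.16 and 2.20. Used at every one of 8 to 20 weekly reviews, they would give about 9–13% two-sided, or about 4–6% for harm alone. The second range is conditional and should not be read as a property of the plan.

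These figures assume a normally distributed test statistic, safety information that accrues in step with recoveries and, for the weekly case, equal spacing and the stated number of looks. The efficacy type I error is unaffected. Nor does a looser standard for harm count as an error: it is a stated choice, and so would be having no boundary, provided both documents said so.

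**What to change.** Reconcile Protocol 9.4.6.1, 9.4.6.2 and 10.1.6.2 with SAP 6.6.1 and 6.6.2, in one of two ways:

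1. Keep a harm guide. Recompute the Pocock-type bounds for the formal looks actually scheduled (2.16 and 2.20 if these are 50% and final, at 5% two-sided). Name the endpoint, the test statistic and the error rate, and state that weekly reviews carry no boundary.
2. Keep no boundary. Delete the z-scores and state in both documents that safety is reviewed without a formal boundary.

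Because the interim review has already taken place, a change of wording cannot alter it. The CSR should therefore report which guide, if any, the DSMB used for safety and at which reviews. The cost is wording in the protocol, the SAP and the DSMB guidance, plus a short statement in the CSR. No patients or new data are needed.

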9.4.6.2 Interim Efficacy Review

The Lan-DeMets spending function analog of the O'Brien-Fleming boundaries will be used to monitor the primary endpoint as a guide for the DSMB for an overall two-sided type-I error rate of 0.05. Interim efficacy analyses will be conducted after the blinded sample size re-estimation of the primary efficacy endpoint at approximately 33%, 67%, and 100% of total information.

Conditional power will be presented as an additional guide to the DSMB. Conditional power allows computation of the probability of obtaining a statistically significant result by the end of the trial given the data accumulated thus far, incorporating and assuming a hypothesized treatment effect (e.g., the treatment effect assumed for sample size determination) thereafter. If conditional power is less than 20% under the original trial assumptions, consideration should be given to stopping the trial.

The unblinded statistical team will prepare these closed reports for DSMB review and recommendations. Analyses will be presented with blinded codes for treatment arms to protect against the possibility that the DSMB report may fall into the wrong hands. A DSMB charter will further describe procedures and membership. An additional document on statistical issues related to monitoring will be provided to the DSMB prior to interim analyses.

9.4.7 Sub-Group Analyses

Subgroup analyses for the primary outcomes will evaluate the treatment effect across the following subgroups: geographic region, duration of symptoms prior to enrollment, age, sex and comorbidities. A forest plot will display confidence intervals across subgroups. Interaction tests will be conducted to determine whether the effect of treatment varies by subgroup.

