8.1.2. Supplemental and Sensitivity Analyses

For all supplemental and sensitivity analyses of the primary outcome, p-values will not be reported, and 95% confidence levels will be used for confidence interval estimates.

The primary analysis will be repeated in the Treated analysis population where subjects who are ineligible at baseline will be censored at enrollment. The tabular and graphical summaries described in the previous section will be replicated for this Treated analysis.

Sensitivity analyses will be performed using Cox proportional hazards models to estimate the hazard ratio. First, an ITT analysis will be performed in which subjects who die prior to recovering are treated as experiencing a competing risk in the Fine-Gray proportional hazards regression model. Second, a Cox model will be fit with binary indicators for treatment group and disease severity (Mild/Moderate vs. Severe [separate models for randomized stratum and actual stratum]) as well as a treatment * disease severity interaction term. The models will be fit to the ITT analysis population. The treatment group hazard ratios and CIs will be reported for both sets of models and the interaction term p-value will be reported for the interaction models.

The primary analysis will also be repeated using the other subgroups defined in Section 6.4 in place of disease severity. Each subgroup will be considered separately and the tabular and graphical summaries described in the previous section will be replicated for each subgroup. The tabular summary will also include results from an analysis of time to recovery controlling for age and duration of symptoms as continuous covariates. A forest plot will be generated to display the overall treatment hazard ratio estimate and CI from each of the within-stratum analyses (Figure 6). These analyses will be performed in the ITT and Treated populations.

In addition, a forest plot will be generated for the “leave one out” sensitivity analyses described in Section 6.7; hazard ratio estimates and CIs will be provided for each subgroup that leaves a single site out.

An additional sensitivity analysis will evaluate the effect of recoveries that were not sustained as indicated in Section 3.3.2.

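### The protocol promises interaction tests for five named subgroup factors, but the SAP specifies an interaction term only for disease severity, so none of the five gets its test

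*Protocol*

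**What the plan says.** Protocol 9.4.7 plans subgroup analyses of the primary outcome by "geographic region, duration of symptoms prior to enrollment, age, sex and comorbidities", displayed in a forest plot. It adds, without exception, that "Interaction tests will be conducted to determine whether the effect of treatment varies by subgroup".

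SAP 6.4 widens the list to seven factors by adding race and severity, and several factors appear in more than one grouping. SAP 8.1.2 then does three things for the primary outcome:

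- It opens with a general rule: "p-values will not be reported, and 95% confidence levels will be used for confidence interval estimates".
- It fits a Cox model with treatment and mild/moderate versus severe disease "as well as a treatment * disease severity interaction term". There are "separate models for randomized stratum and actual stratum", and "the interaction term p-value will be reported for the interaction models". The programming note for Table 15 puts that p-value in a footnote.
- For the remaining subgroups it repeats the primary analysis within levels: "Each subgroup will be considered separately and the tabular and graphical summaries described in the previous section will be replicated for each subgroup". A forest plot follows. Age and symptom duration also enter one model as continuous covariates, with no interaction term.

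The SAP's summary of changes (Section 15, version 2.0 to 3.0) records that subgroups were added. It does not mention removing interaction tests.

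**The concern.** Severity is the only factor with an interaction test, and it is not one of the five factors the protocol names. A team that follows the SAP as written therefore delivers none of the tests the protocol commits to.

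The interaction test is the valid way to ask whether effects differ between subgroups. Without it, readers of the forest plot have only separate intervals to compare, and the natural comparison is whether an interval crosses 1 in one row and not in another. When the benefit is the same in everyone, that pattern arises often, simply because the rows hold different numbers of events.

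**Working it through.** **1. Count of rows and groupings in SAP 6.4 (primary outcome).**

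| Factor | Groupings | Rows | Named in Protocol 9.4.7 | Interaction test in SAP 8.1.2 |
|---|---|---|---|---|
| Region | 2 | 2 + 3 = 5 | yes | no |
| Symptom duration | 3 | 4 + 2 + 2 = 8 | yes | no |
| Comorbidities | 3 | 2 + 3 + 2 = 7 | yes | no |
| Age | 1 | 3 | yes | no |
| Sex | 1 | 2 | yes | no |
| Race | 1 | 4 | no | no |
| Severity, randomised and actual | 2 | 2 + 2 = 4 | no | yes |
| Baseline ordinal category | 1 | 4 | no | no |

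Total: 37 rows in 14 groupings. Named in the protocol: 5 + 8 + 7 + 3 + 2 = 25 rows in 10 groupings, none tested. Without a test overall: 37 − 4 = 33 rows in 14 − 2 = 12 groupings.

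**2. The plan's own design figure.** Protocol 9.2 gives E = 4(1.96 + z)² / (ln θ)². With θ = 1.35 and 85% power (z = 1.036), E = 4 × 2.996² / 0.3001² ≈ 399, against the stated 400. The same approximation, with the standard error of a log rate ratio equal to 2/√E under 1:1 allocation, is used below.

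**3. How often two rows disagree when the effect is uniform.** Take a true ratio of 1.35 everywhere (ln 1.35 = 0.3001) and 400 recoveries. The documents give no subgroup shares, so the splits are assumptions. For each row, P(interval excludes 1) = Φ(0.3001/SE − 1.96). The two rows are independent, so the probabilities multiply.

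| Split | Events | SE | Smaller row's CI includes 1 | Larger row's CI excludes 1 | Both |
|---|---|---|---|---|---|
| 25:75 | 100 and 300 | 0.200 and 0.115 | 0.677 | 0.739 | 0.50 |
| 10:90 | 40 and 360 | 0.316 and 0.105 | 0.844 | 0.812 | 0.69 |

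A 5% interaction test would wrongly signal a difference in about 5% of such trials.

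**4. A larger trial.** The protocol says enrolment may exceed 800, and Section 9 assumes 70% recovery, so 800 × 0.70 = 560 recoveries. At 25:75 (140 and 420 events) the product is 0.573 × 0.868 = 0.50. At 10:90 (56 and 504 events) it is 0.799 × 0.920 = 0.74. More events do not remove the problem.

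**5. What the restored tests can do.** The standard error of the log ratio of rate ratios is √(4/E₁ + 4/E₂). At 400 recoveries split 50:50 it is √(4/200 + 4/200) = 0.200. Power for a ratio of rate ratios of 1.35 is Φ(0.3001/0.200 − 1.96) = 32%, and 85% power needs exp(0.200 × 2.996) = 1.82. At splits of 30:70, 20:80 and 10:90, power for 1.35 is 28%, 22% and 15%.

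**6. False positives if the tests were independent.** Five tests at 5% give 1 − 0.95⁵ = 23%, twelve give 46% and fourteen give 51%. The groupings overlap, so these are guides only.

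**The case against.** The strongest reply is that this is a narrow mismatch with limited consequences. The SAP nowhere says that overlap with 1 will be used to infer different effects. The forest plot gives each hazard ratio and interval, from which a two-level interaction can be approximated. Withholding p-values within subgroups discourages a significant-here, not-there reading. The tests would have little power. All of this is fair, and it limits the seriousness of the point. It does not remove the gap: the protocol made a commitment, the SAP does not carry it out, and the SAP's log gives no reason. Low power argues for reporting the ratio of effects with its interval rather than leaving readers to compare rows by eye.

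Four stronger readings are tempting and are not supported:

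- *No subgroup row is tested.* The four randomised and actual severity rows have an interaction p-value. The count without one is 33, not 37. Race and baseline ordinal category are SAP additions, so their lack of a test breaks no promise.
- *The SAP suppresses subgroup p-values generally.* The sentence "For all supplemental and sensitivity analyses of the primary outcome, p-values will not be reported" covers the primary outcome only. The Day 15 subgroup shell (Table 23) has a p-value column, although for the treatment effect and not for an interaction.
- *Readers would be misled in 68% or 84% of trials.* Those figures (0.677 and 0.844 above) are the chance that one small row's interval includes 1, which is low subgroup power. The discordant pattern has probability 50% or 69%.
- *The promise extends to Day 15 or to every SAP grouping.* Protocol 9.4.7 concerns the primary outcome and five factors.

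**Conclusion.** The point holds as a protocol–SAP discrepancy for the primary outcome. None of the five factors named in Protocol 9.4.7 has an interaction test in the SAP: 25 rows in 10 groupings, within 33 untested rows in 12 groupings overall. Section 15 of the SAP does not record a removal, though it covers only the step from version 2.0 to 3.0.

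Under a uniform ratio of 1.35 and 400 recoveries, discordant intervals would appear in about half of trials for a 25:75 split and about 69% for a 10:90 split. Those figures rest on assumed event shares and the usual large-sample approximation; the counts rest on the documents alone. The primary test and its type I error are unaffected. What is at stake is how the subgroup results are read. The change should be made because it is cheap and restores an analysis already committed to.

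**What to change.** In SAP 8.1.2, add a treatment-by-subgroup term, with the subgroup main effect, to the severity-stratified Cox model for each of the five protocol-named factors. Use one grouping per factor, chosen in advance; testing all the overlapping cuts of symptom duration and comorbidity would only multiply false positives. Because version 3.0 was written after the interim results became public, record when the groupings were chosen and whether subgroup results had been seen. Baseline ordinal category may be added as an option.

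On the forest plot, report the ratio of hazard ratios with its 95% interval and the interaction p-value (one joint p-value where a factor has more than two levels), labelled exploratory and unadjusted. State that these p-values are exempt from the no-p-value rule at the start of 8.1.2, as the severity interaction already is in effect. Say in the text that a non-significant test does not show that effects are the same.

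Reconcile the shells: Tables 16 and 17 follow the format of Table 14, which has a P-value column that 8.1.2 rules out.

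If the sponsor prefers not to run the tests, the alternative is to record and justify dropping them. Doing the same for Day 15 is optional.

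The cost is one model term per factor, one forest-plot column and a few sentences. No new data are needed.
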